10.1.3.3 Summary of Efficacy Variables

The raw value and change from baseline in ppFEV₁, SwCl and CFQ-R will be summarized descriptively (n, mean, SD, median, minimum, and maximum) at baseline and post-baseline visits. For the IA purpose, a visit will be included in the summary if there are ≥ 20 subjects with available data from each treatment group at that visit.

10.1.4 Safety Analysis

Safety analyses specified in Section 9.4 will be performed during the IA based on the IA Safety Set.

10.1.4.1 Additional Safety Analysis

The following safety summaries will be performed during the IA based on the Safety Set, as well as for subjects in the Safety Set who had been on-study for ≥ 12 weeks.

- An overview of all TEAEs by treatment group and overall which includes the following categories:
 - Number of TEAEs (total number of TEAEs only)

- Subjects with any TEAEs
- Subjects with TEAEs by strongest relationship
- Subjects with TEAEs by maximum severity
- Subjects with TEAEs leading to study drug discontinuation
- Subjects with TEAEs leading to study drug interruption
- Subjects with Grade 3/4 TEAEs
- Subjects with related TEAEs
- Subjects with serious TEAEs
- Subjects with related serious TEAEs
- Subjects with TEAE leading to death
- Summaries of TEAEs by MedDRA SOC and PT using frequency counts and percentages, presented by treatment group, for the following:
 - All TEAEs
 - Grade 3/4 TEAEs
 - TEAEs leading to treatment discontinuation
 - TEAEs leading to treatment interruption
 - Serious TEAEs
- A summary of TEAEs by PT
- Analysis of adverse events of special interest (see Section 9.4.7.1)
- Threshold analysis for the LFT laboratory test (see Section 9.4.2)

10.2 DMC Analysis

The DMC will conduct planned safety/efficacy review(s) of study data as outlined in the DMC charter. For the open session of each DMC meeting, selected tables will be presented for the overall treatment group based on the blinded data. For the closed session, the presentation will be by treatment group based on the unblinded data (generated by the independent biostatistician).

The timing of DMC meetings is outlined in Table 10-1.

Table 10-1 DMC Meeting Schedule

Meeting	Timing
Organizational	Teleconference prior to start of the study
First Planned Review	After ≥ 50 subjects have completed Week 4
Second Planned Review	Interim analysis of safety and efficacy after ≥ 140 subjects have completed the Week 4 visit and after ≥ 100 subjects have completed the Week 12 visit.
Ad-hoc	Teleconference on an as-needed basis

10.2.1 DMC Safety/Efficacy Review

To protect the integrity of the treatment assignment and study data, the following steps for the flow of data will be executed for the DMC review:

1. The Vertex Biometrics Department will prepare the SAS codes, SDTM/ADaM data sets, and blinded outputs (tables, figures and listings) of safety and efficacy data using dummy treatment codes, dummy (unrestricted) spirometry data, and dummy (unrestricted) sweat chloride data;
2. The IWRS vendor, [REDACTED] will provide the unblinded treatment codes to the independent biostatistician via a secure file transfer protocol, the independent biostatistician will verify the treatment assignment against the randomization list generated by [REDACTED]
3. The spirometry vendor will provide the restricted spirometry data directly to the independent biostatistician, via a secure file transfer protocol;
4. The sweat chloride vendor will provide the restricted sweat chloride data directly to independent biostatistician, via a secure file transfer protocol;
5. The independent biostatistician will generate the unblinded outputs (tables, figures and listings) and provide them directly to the DMC team for their review, via a secure file transfer protocol.
6. The Vertex Biometrics Department will generate any blinded outputs (tables, figures and listings), for the open sessions of the DMC meetings, as applicable.

12 LIST OF APPENDICES

Appendix A: Analysis Visit Windows for Safety and Efficacy Assessments

Table 12-1 Analysis Visit Windows for Safety and Efficacy Assessments			
Assessment	Visit¹	Target Study Day	Analysis Visit Window (in study days)^{2,3}
Safety Assessment			
Serum Chemistry Hematology	Day 1 (Baseline)	1	≤1 Pre-dose
	Day 15	15	[1, 22]
	Week 4	29	(22, 43]
	Week 8	57	(43, 71]
	Week 12	85	(71, 99]
	Week 16	113	(99, 141]
	Week 24	169	(141, 183]
Safety Follow-up	Not applicable		Use nominal visit
Standard 12-lead ECG	Day 1 (Baseline)	1	≤1 Pre-dose
	Day 15 Pre-dose and Postdose	Not applicable	Use nominal visit
	Week 4	29	(22, 43]
	Week 8	57	(43, 71]
	Week 12	85	(71, 99]
	Week 16	113	(99, 141]
	Week 24	169	(141, 183]
Safety Follow-up	Not applicable		Use nominal visit
Vital Signs (excluding BMI, Weight, Height and their Z-scores)	Day 1 (Baseline)	1	≤1
	Day 15	15	[1, 22]
	Week 4	29	(22, 43]
	Week 8	57	(43, 71]
	Week 12	85	(71, 99]
	Week 16	113	(99, 141]
	Week 24	169	(141, 183]
Safety Follow-up	Not applicable		Use nominal visit
Coagulation	Day 1 (Baseline)	1	≤1 Pre-dose
	Week 24	169	[1, 183]
	Safety Follow-up	Not applicable	Use nominal visit
Efficacy Assessment and Pharmacodynamic Assessment			
Spirometry	Day 1 (Baseline)	1	≤1 Pre-dose
	Day 15	15	(1, 22]
	Week 4	29	(22, 43]
	Week 8	57	(43, 71]
	Week 12	85	(71, 99]
	Week 16	113	(99, 141]
	Week 24	169	(141, 183]
Safety Follow-up	Not applicable		>183

Assessment	Visit¹	Target Study Day	Analysis Visit Window (in study days)^{2,3}
Sweat Chloride	Day 1 (Baseline)	1	≤1 Pre-dose
	Week 4	29	(1, 43]
	Week 8	57	(43, 71]
	Week 12	85	(71, 127]
	Week 24	169	(127, 183]
CFQ-R	Day 1 (Baseline)	1	≤1
	Week 4	29	(1, 43]
	Week 8	57	(43, 71]
	Week 12	85	(71, 99]
	Week 16	113	(99, 141]
	Week 24	169	(141, 183]
	Safety Follow-up	Not applicable	>183
Weight, Height and BMI (and the corresponding z-score)	Day 1 (Baseline)	1	≤1
	Day 15	15	(1, 22]
	Week 4	29	(22, 43]
	Week 8	57	(43, 71]
	Week 12	85	(71, 99]
	Week 16	113	(99, 141]
	Week 24	169	(141, 183]
	Safety Follow-up	Not applicable	>183

Notes:

¹ Visit name for analysis purpose is used to report data in tables and figures.

² The analysis visit windows will be applied using the following rules for both scheduled and unscheduled visits:

- a. If no numerical measurement is available within a visit window, the measurement will be considered missing for the visit.
- b. If there is more than 1 numerical measurement available within a visit window, use the following rules:
 - i. The measurement closest to the target day will be used; or
 - ii. If there are multiple measurements with the same distance from the target day, the latest measurement will be used.

³ For lab, ECG and vital sign measurement collected on the date of first dose of study drug, if it cannot be determined whether the measurement is before or after the first dose:

- a. Scheduled measurement will be treated as pre-dose observation.
- b. Unscheduled measurement will be treated as post-dose observation.

Derived Variables:

1. Age (in years) at first dose date and nominal visit (for demographics, listing and the calculation of [percent] predicted spirometry variables):

Obtain the age at informed consent (in days) in “yy, mm” format (e.g., 24 years, 6 months) from the Vital Signs (VS) page at the Screening Visit, and add 0.5 month to convert to days.

Obtain the informed consent date.

Then age (in years) at first dose or nominal visit = [(first dose date or nominal visit date – informed consent date) in days + age at informed consent (in days)]/365.25.

Table 12-1 Analysis Visit Windows for Safety and Efficacy Assessments			
Assessment	Visit¹	Target Study Day	Analysis Visit Window (in study days)^{2,3}
2.	Age (in months) at nominal visit (for use in calculation of BMI and weight z-score):		
	Obtain the age at informed consent (in months) in “yy, mm” format (e.g., 24 years, 6 months) from Vital Signs (VS) page at the Screening Visit.		
	Obtain the informed consent date.		
	Then age (in months) at nominal visit = integer part of $\{[(\text{age at informed consent (in months)} + 0.5 + \text{diff}(\text{first dose date or nominal visit date, informed consent date}) \text{ in months})] + 0.5$.		
3.	Missing first dose date or last dose date		
	If the first dose date is missing, use Day 1 visit date to impute.		
	If the last dose date is missing or partial date is reported, the last dose date will be imputed based on, in descending order priority, the Early Treatment Termination (ETT) visit date, last visit date before the Safety Follow-up, or the last study drug administration date from EX SDTM domain, as appropriate. The imputation algorithm will ensure the imputed last dose date does not exceed the study participation end date.		
4.	Sweat Chloride:		
	Non-missing sweat chloride concentrations from the left arm and right arm with assessment end date/time for a given arm up to 30 minutes after first dose time in treatment period will be considered for baseline.		
5.	Electrocardiogram:		
	Baseline is defined as the most recent pretreatment measurement before the first dose of study drug in the Treatment Period. If multiple ECG measurements are obtained on the same calendar day during the TE period,		
	
 ○ For summary purpose, the calculated average ECG will be used as the ECG value on that day (except for Day 15 visit); ○ For threshold analysis purpose, all reported ECG values will be used. 		

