11.6 Efficacy

11.6.1 Spirometry

Spirometry will be performed according to the American Thoracic Society Guidelines/European Respiratory Society Guidelines¹⁰ and according to the additional guidelines that follow.

Pre-bronchodilator spirometry is defined as spirometry testing performed for subjects who have

- withheld their short-acting bronchodilators (e.g., albuterol) or anticholinergic (e.g., ipratropium bromide [Atrovent[®]]) for more than 4 hours before the spirometry assessment;
- withheld their long-acting bronchodilator (e.g., salmeterol) for more than 12 hours before the spirometry assessment; and
- withheld their once-daily, long-acting bronchodilator (e.g., tiotropium bromide [Spiriva[®]]) for more than 24 hours before the spirometry assessment.

During the Screening Period, spirometry assessments may be performed pre- or post-bronchodilator. At all other visits, all spirometry assessments should be performed pre-bronchodilator. During the Treatment Period, spirometry assessments must be performed before study drug dosing ([Section 9.6.1](#)) at approximately the same time at each visit. In the event that a subject forgets to withhold bronchodilator(s), spirometry should be performed according to the following:

- If a subject's Day 1 spirometry assessment is pre-bronchodilator, but, on a subsequent visit, the subject forgets to withhold bronchodilator use, a post-bronchodilator spirometry assessment will be obtained for that visit only, and the visit will not be rescheduled.
- If, on Day 1, the subject forgets to withhold his/her dose of bronchodilator, spirometry should be performed post-bronchodilator, and all subsequent spirometric measurements (according to the schedule of assessments in [Table 3-2](#)) should be performed post-bronchodilator.
- Each spirometry assessment will be recorded in the source documents as pre- or post-bronchodilator.

All sites will be provided with spirometers to be used for all study assessments. Spirometry data will be transmitted to a centralized spirometry service for quality review. The investigator's assessment of the spirometry results will be used for the screening assessment and determination of eligibility.

See [Section 10.7.1](#) for information about access to spirometry results.

The measured spirometric values listed below will be converted to percent predicted values using the standard equations of GLI.⁹

- FEV₁ (L)

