11.6.4 Other Events Related to Outcome

11.6.4.1 Antibiotic Therapy for Sinopulmonary Sign/Symptoms

New or changed antibiotic therapy (IV, inhaled, or oral) for the following sinopulmonary signs/symptoms will be determined and documented at visits as indicated in [Table 3-2](#):

- Change in sputum
- New or increased hemoptysis
- Increased cough
- Increased dyspnea
- Malaise, fatigue, or lethargy
- Temperature above 38°C (equivalent to approximately 100.4°F)
- Anorexia or weight loss
- Sinus pain or tenderness
- Change in sinus discharge
- Change in physical examination (PE) of the chest
- Decrease in pulmonary function by 10%
- Radiographic changes indicative of pulmonary infection

For this study, PEx is defined as a new or change in antibiotic therapy (IV, inhaled, or oral) for any 4 or more of the above signs/symptoms. This definition is based on the definition of a PEx used in previous clinical studies, including IVA clinical studies.^{20, 21}

It is recommended that the study drug not be interrupted during a PEx unless, in the opinion of the investigator, it would be in the best interest of the subject.

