A key secondary endpoint is the absolute change in ppFEV₁ from baseline through Week 24. Assuming a within-group SD of 7 percentage points and a 10% dropout rate at Week 24, a sample size of 180 subjects in each treatment group will have approximately 99% power to detect a difference between the treatment groups of 5.0 percentage points for the absolute change in ppFEV₁ from baseline through Week 24, based on a 2-sided, 2-sample *t*-test at a significance level of 0.05.

A key secondary endpoint is the number of PEx through Week 24. Assuming a rate of PEx for the placebo group of 0.6 over 24 weeks and a 10% dropout rate, with 180 subjects and the overdispersion parameter of 0.5 in each treatment group, the power to detect a 40% reduction in the PEx rate for VX-445/TEZ/IVA group compared to placebo group is approximately 80%, based on a 2-sided, 2-sample negative binomial regression model test for the ratio of rates, at a significance level of 0.05.

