9.1 General Considerations

The Schedule of Assessments is provided in Section 3 of CSP. The precision standards for reporting safety and efficacy variables are provided in an internal Biometrics document that specifies the programming rules including the precision for derived variables.

Continuous variables will be summarized using the following descriptive summary statistics: the number of subjects (n), mean, SD, median, minimum value (min), and maximum value (max).

Categorical variables will be summarized using counts and percentages. Percentages will be presented to 1 decimal place.

Baseline value, unless otherwise specified, is defined as the most recent non-missing measurement (scheduled or unscheduled) collected before the first dose of study drug in the Treatment Period.

Absolute change from baseline will be calculated as post-baseline value - baseline value.

Relative change from baseline will be calculated as (post-baseline value - baseline value)/baseline value.

Treatment-emergent (TE) period will include the time from the first dose of study drug in the Treatment Period until 28 days after the last dose of study drug or to the completion of study participation, whichever occurs first.

Unscheduled visits: Unscheduled visit measurements will be included in analysis as follows:

- 1) In scheduled visit windows per specified visit windowing rules
- 2) In the derivation of baseline and last on-treatment measurements
- 3) In the derivation of maximum and minimum values during TE period, and maximum and minimum change from baseline values during TE period for safety analyses
- 4) In individual subject data listings as appropriate

Visit windowing rules: The analysis visit windows for protocol-defined visits are provided in [Appendix A](#).

Incomplete/missing data will not be imputed, unless otherwise specified.

Outliers: No formal statistical analyses will be performed to detect or remedy the presence of statistical outliers, unless otherwise specified.

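### The SAP visit-window rule gives a scheduled visit no priority, so an unscheduled or early-termination spirometry nearer Day 29 can replace a valid scheduled Week 4 value; the likely effect is small and the remedy free

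*SAP*

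**What the plan says.** SAP 9.1 brings unscheduled measurements into the analysis "In scheduled visit windows per specified visit windowing rules". Those rules are in SAP Appendix A, Table 12-1. Note 2 opens: "The analysis visit windows will be applied using the following rules for both scheduled and unscheduled visits". When a window holds more than one value, note 2b decides: "The measurement closest to the target day will be used; or" and then "If there are multiple measurements with the same distance from the target day, the latest measurement will be used".

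For spirometry, Week 4 has target Day 29 and window (22, 43], that is, Days 23 to 43. Protocol Table 3-2 allows the Week 4 visit ±5 days, that is, Days 24 to 34. The Early Termination of Treatment (ETT) visit has no row in Table 12-1, so its measurements are placed by study day like any other. Protocol 9.1.4 requires subjects who stop treatment to keep attending the scheduled visits after the ETT Visit, so a subject can have both an ETT value and a scheduled value in one window.

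The same note governs the later spirometry visits and weight, height and BMI. SAP 10.1.1 carries the final-analysis conventions over to the interim analysis, where the primary endpoint may be decided.

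**The concern.** A scheduled value is fixed by the calendar. An unscheduled one may be taken because the subject is unwell, and an ETT value because treatment has stopped. If such a value happens to lie nearer Day 29, the scheduled value is dropped although it was obtained within the protocol window. For example, with the scheduled Week 4 spirometry on Day 34 and an extra test on Day 31, the Day 31 value becomes the primary-endpoint observation.

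Where illness prompts the test, selection depends on outcome. It is plausible that some suspected pulmonary exacerbations (PEx) lead to spirometry, because one of the 12 signs and symptoms in Protocol 11.6.4.1 is "Decrease in pulmonary function by 10" per cent. If such tests follow PEx, and PEx are rarer on active treatment, replacement would be commoner on placebo.

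No planned analysis would show this. SAP 9.3.1.3 plans no supportive analysis of the primary endpoint, and the one sensitivity analysis (SAP 9.3.1.4) is multiple imputation for missing data, run only if at least 10% of values are missing in an arm.

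**Working it through.** **1. The plan's own figures.** Interim power for the primary endpoint (SAP 7.2): n = 70 × 0.95 = 66.5 per arm, SD 7, difference 5.0, two-sided alpha 0.044. SE = 7 × √(2/66.5) = 1.21; power = Φ(5/1.214 − 2.014) = 98.2% (98.1% with the noncentral t). The plan says about 98%, so it reproduces.

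PEx power: the SAP states "Assuming a rate of PEx for the placebo group of 0.6 over 24 weeks and a 10% dropout rate" and "the power to detect a 40% reduction in the PEx rate for VX-445/TEZ/IVA group compared to placebo group is approximately 80" per cent. The active rate is 0.6 × (1 − 0.4) = 0.36. With n = 180 × 0.9 = 162 and overdispersion 0.5, the variance of the log rate ratio is (1/0.6 + 1/0.36 + 2 × 0.5)/162 = 0.0336, SE 0.183. Power = Φ(0.511/0.183 − 1.96) = 79.6%, which also reproduces. The two PEx rates are used below.

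**2. Days on which another value wins.** For each scheduled day, count the other days that are closer to Day 29, or equally close and later:

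| Scheduled Week 4 day | 24 | 25 | 26 | 27 | 28 | 29 | 30 | 31 | 32 | 33 | 34 |
|---|---|---|---|---|---|---|---|---|---|---|---|
| Displacing days | 10 | 8 | 6 | 4 | 2 | 0 | 1 | 3 | 5 | 7 | 9 |

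The mean is 55/11 = 5.0. Day 24 is the least favourable day, because a tie on Day 34 also wins. A scheduled value on Day 29 can be displaced only by a later measurement on the same day.

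**3. Share displaced.** P = 1 − exp(−rate × share of PEx tested × days/168). Assumptions, none of them in the documents: unscheduled spirometry follows PEx at the planning rates; scheduled days are uniform over Days 24 to 34 (5.0 displacing days); 50–100% of PEx have one test.

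- All PEx tested: placebo 1 − exp(−0.6 × 5/168) = 1.77%; active 1 − exp(−0.36 × 5/168) = 1.07%; difference 0.70 percentage points. In 180 subjects per arm: 3.2 and 1.9.
- Half tested: 0.89% and 0.53%; difference 0.35 percentage points.
- All tested, every visit on Day 24 (10 days): 3.5% and 2.1%; difference 1.39 percentage points.

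**4. Shift in the treatment difference** = difference in shares × drop in ppFEV₁, with the drop assumed to be 5–10 points.

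- Uniform days: from 0.0035 × 5 = 0.02 to 0.0070 × 10 = 0.07 points.
- All visits on Day 24, all PEx tested, 10-point drop: 0.0139 × 10 = 0.14 points.
- Stress test, three tests per PEx and a drop of 5–15 points: 0.10–0.31 with uniform days, 0.20–0.59 with every visit on Day 24.

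**5. Comparison.** The planned difference is 5.0. The SE is 1.21 at the interim and 7 × √(2/171) = 0.76 at the final analysis (5% dropout). A true difference of 4.93 instead of 5.0 would have 98.0% interim power instead of 98.2%. With no true effect, a shift of 0.07 moves the interim rejection rate from 0.0440 to 0.0444.

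**6. Later visits.** Weeks 8, 12, 16 and 24 also have ±5-day visits around the target, inside windows reaching at least 14 days either side, so the day counts are the same. Under the same assumptions, the average through Week 24 would shift by about the same amount. For weight and BMI there is no basis for a size.

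**The case against.** The rule is prespecified, deterministic and blind to treatment, and SAP 9.1 includes unscheduled values deliberately. The protocol names the visits in its model and leaves detail to the SAP, so this is a gap and not a contradiction. That stands.

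Stronger readings are tempting, but the documents do not support them:

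- *That sick-visit spirometry is expected.* Protocol Table 3-2 has no sick visit. A PEx needs any four of twelve signs or symptoms, so it can be recorded without spirometry. The protocol provides for extra ECGs, laboratory tests and symptom-directed examinations, but Protocol 11.6.1 has no such provision for spirometry, and nothing says that routine-care spirometry would enter the database. Such tests are plausible, and no more.
- *That unscheduled tests escape the testing conditions.* Protocol 11.6.1 is not limited to scheduled visits: "At all other visits, all spirometry assessments should be performed pre-bronchodilator". It also requires treatment-period spirometry before dosing.
- *That any bias must favour the drug.* A recovery or repeat test nearer Day 29 could replace a low scheduled value, and with more illness on placebo that would work against the drug. The calculation has no term for it. It also charges the full drop to each replacement, although a subject ill on one day may still be unwell at a scheduled test days later.

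What survives is narrower: the rule does allow replacement, nothing planned would reveal it, and neither document gives a reason to prefer an extra value to a valid scheduled one.

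**Conclusion.** The point holds as a minor one. An unscheduled or ETT spirometry can displace a valid scheduled Week 4 value taken on any day of Days 24 to 34 other than Day 29, and the selection depends on outcome where the extra test was prompted by illness or by stopping treatment.

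The size rests on assumptions about test frequency, visit timing and the drop. Within them the shift is about 0.02–0.07 points in favour of active, and 0.14 at the top of the range with every visit on Day 24. The excess on placebo is an inference from planning rates; with equal rates of extra tests in the two arms there would be no differential. Even the extreme stress case (0.59) is far below 5.0. A reader should not infer that the primary conclusion is at risk, or that the net direction is established.

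**What to change.** In Table 12-1 note 2b, for spirometry and weight/height/BMI, and for the other efficacy assessments for consistency: if a measurement from the nominal scheduled visit lies in the analysis window, use it; use an ETT or unscheduled measurement (closest to target, ties to the latest) only if no nominal scheduled measurement exists in that window.

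ETT should not count as scheduled here. It is triggered by stopping treatment, and it would otherwise still displace the Week 4 value that Protocol 9.1.4 requires.

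The cost is one sentence in an SAP amendment and one sort key in the program, made before the interim data lock and unblinding. Displacement of scheduled values falls to zero in both arms. Sample size, alpha and planned power do not change, and extra values still fill windows that would otherwise be empty. Table 12-1 already has precedents: note 3 separates scheduled from unscheduled measurements, and the Day 15 ECG uses the nominal visit. If the sponsor prefers to keep the present rule, a scheduled-visits-only sensitivity analysis of the primary endpoint would at least show its effect.
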